### **3.9 End of Study**

For the purpose of this protocol, end of study is defined as the completion of the Last Subject Last Visit (LSLV).

## 4. SELECTION OF STUDY POPULATION

### 4.1 Inclusion Criteria

In order to participate in this study, all subjects must meet ALL of the inclusion criteria described.

1. Healthy, non-pregnant subjects who have received a single 5 µg dose of GBS Trivalent Vaccine or placebo in the V98\_06 study and healthy non-pregnant female subjects aged 22-46 years inclusive on the day of informed consent who have not received any GBS vaccine in the past.
2. Individuals who have voluntarily given written informed consent after the nature of the study has been explained according to local regulatory requirements, prior to study entry.
3. Individuals in good health as determined by the outcome of medical history, physical examination and clinical judgment of the investigator.
4. Individuals who can comply with study procedures including follow-up.
5. Females of childbearing potential who are using an effective birth control method which they intend to use until the end of the study (day 181 visit) or females of non-childbearing potential.

### 4.2 Exclusion Criteria

1. Progressive, unstable or uncontrolled clinical conditions.

---

 A subject is considered to be compliant if the Investigator judges that the subject will complete the Subject Diary/ return for all the follow-up visits/ be available for telephone calls as scheduled in the study.

 The following birth control methods are considered effective:

- Abstinence
- Hormonal contraceptive (such as oral, injection, transdermal patch, implant) if used for at least 30 days prior to informed consent
- Diaphragm with spermicide, tubal occlusion device
- Intrauterine device (IUD)
- Tubal ligation
- Male partner using condom with spermicide
- Male partner having been vasectomized at least six months prior to informed consent

 A female is considered to be of non-childbearing potential only after hysterectomy, bilateral oophorectomy, or iatrogenic ablation of ovarian function.

2. Clinical conditions representing a contraindication to intramuscular vaccination and blood draws.
3. Abnormal function of the immune system resulting from:
  - a. Clinical conditions, including but not limited to known or suspected HIV infection or HIV-related disease, a history of or an active autoimmune disorder (as per the judgment of the Investigator)
  - b. Systemic administration of corticosteroids (PO/IV/IM) for more than 14 consecutive days within 90 days prior to informed consent.
  - c. Administration of antineoplastic and immunomodulating agents or radiotherapy within 90 days prior to informed consent.
  - d. Receipt of immunosuppressive therapy within 90 days prior to informed consent
4. Received immunoglobulins or any blood products within 180 days prior to informed consent.
5. Received an investigational or non-registered medicinal product within 30 days prior to informed consent.
6. Study personnel as an immediate family or household member.
7. Any other clinical condition that, in the opinion of the investigator, might interfere with the results of the study or pose additional risk to the subject due to participation in the study.
8. Individuals who received any other vaccines within 14 days for inactivated vaccines or 28 days for live vaccines prior to enrolment in this study or who are planning to receive any vaccine within 28 days from the study vaccination. Exception - an inactivated influenza vaccine may be administered up to 7 days prior to study vaccination or 7 days after study vaccination.
9. Individuals who anticipate becoming pregnant prior to the end of the study, Day 181 Visit.
10. Individuals who are nursing (breastfeeding).
11. Individuals who have had a previous immunization with a vaccine containing Group B Streptococcus antigens that was not part of V98\_06 study.
12. Individuals with a fever (oral temperature  $\geq 38^{\circ}\text{C}$ ) within 3 days prior to day 1 or use of antipyretics and/or analgesic medications within 24 hours prior to day 1.
13. Individuals with acute or chronic infection(s) that require systemic antibiotic treatment or antiviral therapy, within 7 days prior to day 1.

14. Individuals with a history of severe allergic reactions after previous vaccinations or medications, such as anaphylactic shock, asthma, urticaria, or other allergic reaction or hypersensitivity to any vaccine component or medical equipment including latex used in this study.
15. Individuals with any progressive or severe neurologic disorder, seizure disorder, epilepsy or Guillain-Barré syndrome.
16. Individuals with history of substance or alcohol abuse within the past 2 years.

### **4.3 Criteria for Delay of Vaccination**

There may be instances when individuals meet all eligibility criteria for vaccination yet have a transient clinical circumstance which may warrant delay of vaccination: body temperature elevation ( $\geq 38.0^{\circ}$  C) within 3 days prior to intended study vaccination, or use of antipyretics and/or analgesic medications within 24 hours prior to vaccination. Under such circumstances, a subject may be considered eligible for study enrolment after the appropriate window for delay has passed and inclusion/exclusion criteria have been rechecked, and if the subject is confirmed to be eligible.

## 5. STUDY PROCEDURES

The sections that follow provide an overview of the procedures that are to be followed in enrolling, evaluating, and following subjects who participate in this clinical study. Visits can be either clinic visits or safety follow-up telephone calls, as specified in the Table below and in the [Time and Events Table 3](#)

**Table 5-1 Study Procedures**

Visit Category	Procedures
Pre-vaccination Clinic Visit(s)	Section 5.1 describes procedures to be followed prior to study vaccination: informed consent, screening, enrolment, and randomization
Vaccination Clinic Visit(s)	Section 5.2 describes procedures to be followed during each clinic visit involving vaccination: vaccination, post-vaccination procedures, and post-vaccination reminders
Post-vaccination Visit(s)	Section 5.3 describes follow-up clinic visits and safety follow-up calls
Unscheduled Visit(s)	Section 5.4 describes possible procedures to be followed at unscheduled clinic visit
Study Termination Visit	Section 5.5 describes procedures to be followed at the last study visit for a subject (may include early termination visit)

### 5.1 Pre-vaccination Clinic Visit(s)

This section describes the procedures that must be performed for each potential subject prior to vaccination, including obtaining informed consent, screening and enrolment.

#### 5.1.1 Informed Consent

"Informed consent" is the voluntary agreement of an individual or her legal guardian(s) to participate in research. Consent must be given with free will of choice, and without undue inducement. The individual must have sufficient knowledge and understanding of the nature of the proposed research, the anticipated risks and potential benefits, and the requirements of the research to be able to make an informed decision.

Informed consent following local EC guidance **must** be obtained before conducting any study-specific procedure (i.e., all of the procedures described in the protocol). The process of obtaining informed consent should be documented in the subject source document in addition to maintaining a copy of the signed and dated informed consent.

If a subject is unable to read, an impartial witness should be present during the entire informed consent discussion. An impartial witness is defined as a person who is independent from study conduct, who cannot be unfairly influenced by those involved with the study, who attends the informed consent process if the subject or the subject's legally acceptable representative cannot read, and who reads the informed consent form and any other written information supplied to the subject. After the written informed consent form and any other written information to be provided to subjects, is read and explained to the subject and after the subject has verbally consented to the subject's participation in the study and, if capable of doing so, has signed and personally dated the informed consent form, the witness should sign and personally date the consent form. By signing the consent form, the witness attests that the information in the consent form and any other written information was accurately explained to, and apparently understood by, the subject and that informed consent was freely given by the subject.

### 5.1.2 Screening

After an individual has consented to participate in the study and informed consent is signed, that individual will be given a unique Screening Number manually created by the investigator. The subject's unique Screening Number will be documented in the Screening and Enrolment log. The eligibility of the subject will be determined based on the inclusion and exclusion criteria listed in [section 4, Selection of Study Population](#) and evaluated during this screening procedure.

Prior to study enrolment, demographic data will be collected from the subject, including: race, receipt of diphtheria containing vaccine up to 5 years prior to vaccination in the V98\_06 study (if applicable), receipt of diphtheria containing vaccine between vaccination in the V98\_06 study and enrolment into the V98\_06E1 study (if applicable), receipt of diphtheria containing vaccine up to 5 years prior to the V98\_06E1 study (naive subjects only), whether or not they participated in the parent V98\_06 study and if applicable the Subject ID they were assigned in the parent V98\_06 study.

Medical history will also be collected, including but not limited to any medical history that may be relevant to subject eligibility for study participation such as prior vaccinations, concomitant medications, and previous and ongoing illnesses or injuries. Relevant medical history can also include any medical history that contributes to the understanding of an adverse event that occurs during study participation, if it represents an exacerbation of an underlying disease/pre-existing problem.

If a subject reports they are of non-childbearing potential, the medical history in the form of medical records (verbal medical history only is not sufficient in this case) must be collected prior to vaccination or the subject will have to undergo a urine pregnancy test.

If applicable, prior and concomitant medications or vaccinations taken prior to start of study should be collected (refer to [section 6.5, Prior and Concomitant Medications and Vaccines](#) for further details).

Collect vital signs. Measure height and weight.

Perform pregnancy testing in women of childbearing potential (refer to [section 3.5, Collection of Clinical Specimens](#) for guidance regarding the procedure).

A general physical examination is to be performed by a qualified health care practitioner. “Qualified health care practitioner” refers to any licensed health care professional who is permitted by institutional policy to perform physical examinations and who is identified within the Study Staff Signature Log.

These data will be written in the source document (see [section 9.1, Source Documentation](#)). Should the physical assessment reveal any abnormal values or events, these must be documented in the CRF Adverse Events Form.

Prior to vaccination, approximately 20 mL of blood will be drawn from all subjects for the following testing: serology testing. Refer to [section 3.5, Collection of Clinical Specimens](#).

In the event that the individual is determined ineligible for study participation, she is considered a screen failure. The reason for screen failure must be documented in the Screening and Enrolment log. If the individual is determined to be eligible for the study, she will be enrolled into the study.

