Study Completion Procedures									
Study Termination	Section 5.5								X
	Notes: a Confirm consent form(s) signed prior to any procedures. b Procedure to be performed prior to vaccination c Only for women of child bearing potential								

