## 7. ASSESSMENTS

### 7.1 Safety Assessment

The measures of safety used in this study are routine clinical procedures. They include a close vigilance for, and stringent reporting of, selected local and systemic adverse events routinely monitored in vaccine clinical studies as indicators of reactogenicity.

An adverse event (AE) is defined as any untoward medical occurrence in a subject or clinical investigation subject administered a pharmaceutical product at any dose that does not necessarily have to have a causal relationship with this treatment. Therefore, an AE can be any unfavorable and unintended sign (including an abnormal laboratory finding, for example), symptom, or disease temporally associated with the use of an investigational product, whether or not considered related to the investigational product. This definition includes intercurrent illnesses or injuries and exacerbation of pre-existing conditions.

The period of observation for AEs (or sub-set of AEs as according to the [Time and Events Table 3](#)) extends from the time the subject signs informed consent until he or she completes the specified safety follow-up period (until day 181 visit) or terminates the study early (whichever comes first). AEs occurring after the informed consent form is signed but prior to receiving study vaccine/product will be documented as an adverse event and recorded within source document. However, any AEs occurring prior to receipt of any study vaccine will be analyzed separately from “treatment emergent” AEs (AEs occurring after administration of the first study vaccine).

Adverse events are collected as either solicited or unsolicited adverse events. Solicited events are derived from organized data collection systems, such as Subject Diaries.

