### **7.1.2 Unsolicited Adverse Events**

An unsolicited adverse event is an adverse event that was not solicited using a Subject Diary and that was spontaneously communicated by a subject who has signed the informed consent.

Potential unsolicited AEs may be medically attended (defined as symptoms or illnesses requiring hospitalization, or emergency room visit, or visit to/by a health care provider), or were of concern to the subject. In case of such events, subjects will be instructed to contact the site as soon as possible to report the event(s). The detailed information about the reported unsolicited AEs will be collected by the qualified site personnel during the interview and will be documented in the subject’s records.

Unsolicited AEs that are not medically attended nor perceived as a concern by subjects will be collected during interview with the subject and by review of available medical records at the next visit (see section 5.3, [Post-vaccination Visit\(s\)](#)).

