## **8. STATISTICAL CONSIDERATIONS**

### **8.1 Endpoints**

#### **8.1.1 Primary Endpoint(s)**

##### **8.1.1.1 Primary Safety Endpoint(s)**

The frequency and percentage of subjects with solicited local and systemic AEs from vaccination to day 7 in study V98\_06E1. Time intervals after vaccination that will be summarized are: the first 30 minutes after vaccination, days 1-3 (excluding the first 30 min), days 4-7 and days 1-7 (excluding the first 30 min)..

The frequency and percentage of subjects with any unsolicited AEs from the day of vaccination (day 1 in study V98\_06E1) to day 31.

The frequency and percentage of subjects with SAEs, medically attended AEs, and AEs leading to study withdrawal from vaccination in study V98\_06E1 to day 181.

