#### **8.4.2.1.3 Analysis of Unsolicited Adverse Events**

This analysis applies to all adverse events occurring during the study, judged either as probably related, possibly related, or not related to vaccination by the investigator, recorded in AE CRF, with a start date on or after the date of first vaccination. AE starting prior to the first vaccination will only be listed. The original verbatim terms used by investigators to identify adverse events in the CRFs will be mapped to preferred terms using the MedDRA dictionary. The adverse events will then be grouped by MedDRA preferred terms into frequency tables according to system organ class.

All reported adverse events, as well as adverse events judged by the investigator as at least possibly related to study vaccine, will be summarized according to system organ class and preferred term within system organ class. These summaries will be presented by vaccination group. When an adverse event occurs more than once for a subject, the maximal severity and strongest relationship to the vaccine group will be counted.

Separate summaries will be produced for the following categories:

- Serious adverse events.
- Adverse events that are possibly or probably related to vaccine.
- Adverse event leading to withdrawal.
- Adverse events leading to a medically attended visit.

Data listings of all adverse events will be provided by subject. In addition, adverse events in the categories above will be provided as listed data.

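### The date-only selection rule in 8.4.2.1.3 can count findings made before the day-1 injection in the primary unsolicited-AE percentage, against section 7.1.

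*Combined protocol and SAP*

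**What the plan says.** Five places in the protocol bear on this.

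- **Table 3, Time and Events.** The full physical examination is marked in the day-1 column only, with note b: "Procedure to be performed prior to vaccination". Examination and injection therefore share a calendar date.
- **Section 5.1.2, Screening.** On abnormal findings: "Should the physical assessment reveal any abnormal values or events, these must be documented in the CRF Adverse Events Form". The instruction makes no exception for pre-existing findings and mentions no pre-dose marker.
- **Section 8.4.2.1.3, Analysis of Unsolicited Adverse Events.** The analysis takes events "recorded in AE CRF, with a start date on or after the date of first vaccination", whether or not the investigator judges them related. The next sentence reads: "AE starting prior to the first vaccination will only be listed".
- **Section 7.1, Safety Assessment.** It requires that "any AEs occurring prior to receipt of any study vaccine will be analyzed separately from" treatment-emergent events, which it defines as "AEs occurring after administration of the first study vaccine".
- **Section 8.1.1.1, Primary Safety Endpoint(s).** The unsolicited endpoint is "The frequency and percentage of subjects with any unsolicited AEs from the day of vaccination" to day 31. The other two primary safety endpoints start at vaccination; this one starts at the day of vaccination.

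**The concern.** A calendar date cannot separate before from after on the one day when examination and injection both take place. If the site dates an abnormal finding by the day it was seen, the record carries the vaccination date, sits on the AE form, and satisfies the selection rule, although the vaccine had not been given. An event arising between consent and injection on day 1 is in the same position.

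The figure at stake is a primary safety result. Every subject receives the same vaccine, so there is no concurrent unvaccinated group against which a background of pre-dose findings would cancel. The absolute percentages will be read as the safety profile of the dose, and a pre-dose record counted in error can only raise them.

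**Working it through.** The documents give no AE rate, no rate of abnormal examination findings and no safety power figure, so there is no stated number to reproduce. The check is mainly one of text.

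**Step 1. Apply each rule to each possible timing of an AE-form record.**

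| Record | Date rule, 8.4.2.1.3 | Next sentence, 8.4.2.1.3 (read by event) | Section 7.1 |
|---|---|---|---|
| Onset dated before day 1 | not analysed | listed only | separate |
| Dated day 1, before injection | **analysed** | **listed only** | **separate** |
| Dated day 1, after injection | analysed | analysed | treatment-emergent |
| Dated after day 1 | analysed | analysed | treatment-emergent |

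Only the second row conflicts. The sentence on listing can be read in two ways. If it is simply the complement of the date rule, day-1 pre-dose records are counted and 7.1 is contradicted. If it refers to the moment of injection, it contradicts the sentence before it.

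**Step 2. Look for something else that removes the second row.**

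- The endpoint window in 8.1.1.1 opens on the day of vaccination, so it does not.
- Causality does not, because the analysis includes events judged not related.
- No section specifies an onset time or a before/after-injection marker for AEs.
- No section says whether an examination finding is dated by onset or by detection.
- Section 6.6 does require the time of vaccine administration to be documented in an administration log, so the reference point exists but is not used.

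**Step 3. Who can change the primary percentage.** A subject moves it only if all three hold: she was vaccinated (ineligible subjects are screen failures and outside the Exposed Set); she has a pre-dose record dated day 1; and she has no other unsolicited AE by day 31.

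**Step 4. How the size would depend on unknown rates (illustration only).** Let p be the true proportion of vaccinated subjects with a post-injection unsolicited AE by day 31, and q the proportion with a pre-dose record dated day 1. Both are assumed, and assumed independent. Under the literal date rule:

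observed = p + q(1 − p), so excess = q(1 − p).

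The planned maximum is 5 × 40 + 20 = 220 subjects.

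- q = 0 (pre-dose records kept out): excess 0.
- p = 50%, q = 1%: 0.01 × 0.50 = 0.5 points; 0.005 × 220 = 1.1 subjects.
- p = 35%, q = 5%: 0.05 × 0.65 = 3.25 points; 0.0325 × 220 = 7.15 subjects.
- p = 20%, q = 10%: 0.10 × 0.80 = 8.0 points; 0.08 × 220 = 17.6 subjects.

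These figures show only how the excess behaves. None of the rates is in the documents.

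**The case against.** The strongest reply is that the intent is plain. Both 7.1 and the listing sentence in 8.4.2.1.3 put pre-vaccine events outside the main analysis, and a programmer who reads both would probably exclude them. Several further points limit the effect:

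- Many examination findings will have begun earlier. If dated by onset, the date rule already excludes them.
- Section 7.1.2 describes an unsolicited AE as one "that was spontaneously communicated by a subject who has signed the informed consent", which an examiner's finding does not clearly fit.
- The AE form is not in the documents and may carry an onset time or pre-dose box. The protocol also defers some analysis details to a statistical analysis plan.
- All groups have the same day-1 examination, so there is no evident reason for comparisons between groups to be distorted. No safety success criterion depends on the percentage.

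All of this stands as a limit on the likely size. None of it supplies the missing rule. Intent does not tell a programmer how to split records bearing the same date, and 8.4.2.1.3 selects on AE-form entry and date, not on the 7.1.2 definition.

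A reader might also infer that such records would enter the vaccine-related summaries. The documents point the other way: section 7.1.3 classes an event as not related when the vaccine has not been received, and the related-AE summary takes only possibly or probably related events.

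**Conclusion.** The point holds as a conflict between stated rules. For day-1 pre-dose records, the selection sentence of 8.4.2.1.3 disagrees with section 7.1 and with the intent of the sentence that follows it, and nothing in the documents resolves the disagreement. Such records can therefore be counted in the primary any-unsolicited-AE percentage.

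The direction of any error is upward. Its size cannot be determined from the documents: it is zero if pre-dose records are kept out, and otherwise depends on how sites date findings and on rates that are not given.

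A reader might go further and infer that these findings will be counted and that the endpoint is inflated by a known amount. The documents do not support that. Dating by detection is an assumption. A flat addition of 1/40 = 2.5 points in a full 40-subject group, or 1/20 = 5 points in the naive group, is right only for a subject with no other unsolicited AE; otherwise she adds nothing to the any-AE percentage. A range in points obtained by assuming a rate of abnormal findings merely restates the assumption.

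This is worth correcting because it touches a primary safety endpoint and is cheap to settle. It does not show that the endpoint is biased.

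**What to change.** Reconcile sections 5.1.2, 7.1, 8.1.1.1 and 8.4.2.1.3:

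1. In 8.4.2.1.3, define the analysed events as those with onset after administration of the V98_06E1 vaccine, and align the start of the unsolicited endpoint window in 8.1.1.1 with this.
2. For events dated day 1, classify by onset time or by a before/after-injection tick on the AE form, judged against the injection time already documented under 6.6. List pre-dose records only.
3. In 5.1.2, state that an abnormal finding from the pre-vaccination examination is dated by onset where known and marked as pre-dose.

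Sending such findings to the Medical History CRF instead is an option, but it is not needed once they are marked.

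The cost is a sentence in each affected section and, if the AE form has no onset time or equivalent box, one added field. No visit, sample or sample-size change follows.
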